518 dynamics and biological pathways within the human host that are affected by
519 military-relevant stress and are associated with physical and cognitive performance,
520 and identify novel markers of physiological stress.

521

522 **B5. RESEARCH PLAN**

523

524 **B5.1 Research Design**

525

526 This randomized cross-over study will consist of four sequential phases (SUSOPS 1, Recovery
527 1, SUSOPS 2, and Recovery 2).

528

529 **B5.2 Research Subjects/Population(s)**

530

531 **B5.2.1 Subject Population(s)**

532

533 Healthy, recreationally-active adult men, who are active duty military, will be recruited to
534 participate in this study. Male subjects were chosen because of known sex differences in
535 iron status and absorption and differences in their response to exercise, including the IL-
536 6 response to exercise [62, 63]. Pending the outcomes from this study, future, more
537 targeted studies will be designed to address potential sex-based differences in
538 physiological responses to SUSOPS.

539

540 **B5.2.2 Number of Subjects, Records, and/or Specimens**

541

542 This protocol requires 15 subjects complete testing to provide 80% power to detect
543 significant differences in circulating hepcidin responses between SUSOPS 1 and
544 SUSOPS 2. Up to 60 subjects will be enrolled to account for attrition and screening

545 failures in order to get complete data on 15 subjects. See section B5.8.1 for details on
546 sample size calculations.
547

548 **B5.2.3 Inclusion Criteria**

- 549 • Men who are active duty military, aged 18 – 39 years
- 550 • Weight stable in the past 2 months (\pm 2.27 kg)
- 551 • Healthy without evidence of chronic illness, medication use, or musculoskeletal injury
- 552 as determined by the USARIEM Office of Medical Support and Oversight (OMSO)
- 553 • Recreationally active (2-4 days per week aerobic and/or resistance exercise)
- 554 • Refrain from taking any pain-relievers (e.g., acetaminophen), nonsteroidal anti-
- 555 inflammatory drugs (e.g., aspirin, Advil®, Aleve®, Naprosyn®), or any other aspirin-
- 556 containing product for 10 days before starting and at least 5 days after completing
- 557 the study
- 558 • Refrain from the use of alcohol and nicotine for the duration of the study
- 559 • Willing to refrain from alcohol, smoking any nicotine product (includes e-cigarettes),
- 560 vaping, chewing tobacco, caffeine, and dietary supplement use, and from

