5.7.1.1 FDA-approved device being used in this research according to the approved labeling

SmartPill, Polar Electro heartrate monitor, True Max 2400 ParvoMedics, Fatigue Science ReadiBand™ actigraph, Philips Respironics Actiwatch® Spectrum Plus, InBody 720, and DEXA will be used in research according to approved labeling.

5.7.1.2 FDA-approved device being used in this research in a manner other than its approved labeling

N/A

B5.7.2 Drugs

B5.7.2.1 FDA-approved and used in accordance with the approved labeling

N/A

B5.7.2.2 FDA-approved and used in a manner not in accordance with its approved labeling

N/A

B5.7.2.3 Any drug not approved by the FDA

N/A

B5.8 Statistical Analysis

B5.8.1 Sample Size Estimation

Power analyses were performed using www.biomath.info/power/prt.htm and indicate that 11 participants will provide adequate power (alpha = 0.05, power = 0.8) to detect significant changes in circulating concentrations of IL-6 and hepcidin in response to stress and differences in energy balance. To account for potential attrition (~30% attrition in 16-02-HC), 4 additional subjects are requested for a total of 15 subjects. Data used in calculating samples size estimates (i.e., means and standard deviations) are derived from previous studies that found significant increases in IL-6 and/or hepcidin in 1) male athletes (n=12) after a 7-day training block [103], 2) male athletes (n=9) after two 75 min endurance exercise bouts separated by 3 h of rest [22], 3) male athletes (n=8) after two high-intensity endurance exercise bouts over two days [23], and 4) male athletes (n=11) completing a 1.5 h treadmill run [104]. The outcome measures, means, standard deviations (SD), n, and alpha and power levels are included below:

Study	Outcome	Mean difference	SD of difference	Alpha	Power	n/group
[103]	Hepcidin	4.7	4.9	0.05	0.8	11
	IL-6	2.7	1.3	0.05	0.8	5
[22]	IL-6	4.8	1.8	0.05	0.8	6
[23]	IL-6	3.2	2.0	0.05	0.8	6

[104]	Hepcidin	7	7.4	0.05	0.8	11
	IL-6	9	6.6	0.05	0.8	7

1396
1397
1398
1399
1400
1401
1402
1403
1404
1405
1406
1407
1408
1409
1410
1411
1412
1413
1414
1415
1416
1417
1418
1419
1420
1421
1422
1423
1424

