1455 liberal false discovery rate (e.g., 0.20) may be used to reduce type 2 error rates and
1456 increase power. For microbiome analysis, shotgun sequencing (maximum 50 million
1457 pair end reads) of 15 participants will achieve $\geq 69\%$ power to detect a true difference in
1458 relative abundance of at least 1.5 fold with group coefficient variation 1.3, and false
1459 discovery rate of 0.05. Again, a more liberal false discovery rate (e.g., 0.20) may be
1460 used to reduce type 2 error rates and increase power. Power calculations were
1461 conducted using pairwise distances and PERMANOVA power with respect to effect size.
1462 However, power will be enhanced by correlating the blood mRNA data with other omics
1463 readouts derived from saliva (microRNA-seq, metabolomics and microbiome) and blood
1464 (targeted microRNA and metabolomics), and by temporal sample collection. As such,
1465 we expect that 15 participants will provide adequate power to detect differences in blood
1466 mRNA expression, and gut microbiome community and genome composition between
1467 study phases, and correlations between these parameters and other –omics readouts.

1468 **B5.8.2 Data analysis**

1469
1470
1471 Statistical analyses will be conducted using either SPSS (IBM Corp. Armonk, NY), SAS
1472 9.3 (SAS Institute Inc., Cary, NC), or equivalent. Common descriptive statistics will be
1473 used to describe volunteer characteristics. Shapiro-Wilk tests will be used to determine
1474 normality of data, and transformations will be applied as appropriate to ensure model
1475 assumptions are met. Correlation and multiple regression will be used to evaluate
1476 relationships between study outcomes.

1477 **Primary Objectives**

1478
1479 Linear mixed models will be used to determine main effects of phase (SUSOPS BAL and
1480 SUSOPS NEG BAL), time within phase, and their interaction on inflammation, iron
1481 absorption, mood/cognitive, and measures of muscle, nutritional, and metabolic
1482 homeostasis. If phase by time interactions are observed, a Bonferroni correction will be
1483 applied for multiple comparisons. Statistical significance will be set at $P < 0.05$. To test
1484 for carryover effects a main effect of group (SUSOPS BAL first, SUSOPS NEG BAL first)

1485 and a group-by-phase interaction will be included in initial models. These terms will be
1486 removed if they do not significantly contribute to the overall fit of the model. When

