1487 significant phase-by-time interactions are observed post hoc comparisons will be made
1488 using paired t-tests with Bonferroni corrections.

1489

1490 **Secondary Objectives**

1491 Linear mixed models will be used to examine changes in intestinal permeability and
1492 gastrointestinal transit time. Models will include subject as a random factor, and study
1493 phase as a fixed factor. To test for carryover effects a main effect of group (SUSOPS
1494 BAL first, SUSOPS NEG BAL first) and a group-by-phase interaction will be included in
1495 initial models. These terms will be removed if they do not significantly contribute to the
1496 overall fit of the model. When a significant main effect is observed post hoc
1497 comparisons will be made using paired t-tests with Bonferroni corrections.

1498

1499 Fecal metabolomics data will be visualized using hierarchical average-linkage clustering
1500 and principal components analysis. Bacterial taxonomic data will be visualized using
1501 hierarchical average-linkage clustering and principal coordinates analysis of beta (i.e.,
1502 between samples) diversity scores (e.g., Bray-Curtis, and weighted and unweighted
1503 UniFrac). Alpha (i.e., within-sample) diversity will be calculated for taxonomic data using
1504 Shannon, Simpson and Chao1 indices. Linear mixed models will be used to examine
1505 changes in biomarkers of gut health, fecal metabolite concentrations, and alpha diversity
1506 over time. Models will include subject as a random factor, and study phase, time within
1507 phase, and their interaction as fixed factors. To test for carryover effects a main effect of
1508 group (SUSOPS BAL first, SUSOPS NEG BAL first) and a group-by-phase interaction
1509 will be included in initial models. These terms will be removed if they do not significantly
1510 contribute to the overall fit of the model. Models for bacterial taxa and gene abundance
1511 will be analyzed using the R statistical software package “DESeq2” or equivalent. The
1512 Benjamini-Hochberg correction will be used to control the false discovery rate in
1513 microbiome-specific and metabolite models. Data analysis will be completed using
1514 SPSS, XLSTAT, R, Qiime, or similar software as needed.

1515

1516 Linear mixed models will be used to examine changes in appetite-mediating hormone
1517 concentrations, appetite ratings, food preferences, food choice during recovery (i.e., diet

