1728 study if the volunteer is unwilling or unable to complete study procedures or follow study
1729 diets/exercise prescriptions. An investigator may also withdraw a volunteer if the individual
1730 becomes ill or injured or it would not be in the volunteer's best interest to continue. If the
1731 participant is withdrawn by the investigator or decides to voluntarily withdraw himself, all further
1732 data collection will discontinue, but the data that was collected up to the point of withdrawal may

1733 still be used for analysis. Participants will be compensated for any blood draws they completed
1734 up until that point, and they will be asked to return any study food and/or wrappers, study
1735 supplies that were provided, in addition to any study logs that they had completed up to the
1736 point of withdrawal.

1737

1738 **C4. PRIVACY FOR SUBJECTS**

1739

1740 To protect the volunteer's privacy, all of their research-related records will be labeled or "coded"
1741 with an assigned research volunteer number that will not include their name or any other form of
1742 identifiable information. The principal investigator or project coordinator will keep the link
1743 between volunteer number and the volunteer's research records in a locked cabinet. Any
1744 documents that will require the volunteer's name, such as the consent form, will be kept in a
1745 locked cabinet separate from any research documents that contain the volunteer's ID number.
1746 The principal investigator and project manager are the only people who will be able to match the
1747 research volunteer number with any of their personal identifying information.

1748

1749 When the results of the research are published or discussed in conferences, no information will
1750 be included that would reveal the volunteer's identity to others. If photographs, videos, or audio-
1751 tape recordings of volunteers are used for educational purposes, volunteer identity will be
1752 protected or disguised. All identifiable or recognizable information (e.g., names and faces) will
1753 be covered in any photographs unless volunteers agree to sign a photo release form. If
1754 volunteers do not sign a photo release form, any photographs taken of them will be destroyed.

1755

1756 **C5. CONFIDENTIALITY PROCEDURES FOR RESEARCH RECORDS, DATA, HUMAN** 1757 **BIOLOGICAL SPECIMENS**

1758

1759 All data and medical information obtained will be considered privileged and held in confidence.

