1948 **Research-related Risks:** The DEXA scan is an X-ray and is considered to be a low risk
1949 procedure. The radiation dose of the whole-body DEXA scan is 0.1 mrem. This dose is
1950 equivalent to approximately 1/250 of normal annual background radiation, 1/9 of the
1951 radiation received in a transatlantic flight, or 1/30 of the radiation received in a chest X-
1952 ray.

1953 **Measures to Minimize Risks of Harm:** A quality assurance check will be completed on
1954 the DEXA each day prior to its use; the software will not allow the use of the DEXA
1955 densitometer if the quality assurance check fails.

1956
1957 **There are no risks associated with bio-electrical impedance body composition
1958 measures**

1959
1960 **There are no risks associated with saliva sampling measures**

1961
1962 **Research Procedure Name:** Multi-sugar absorption test for intestinal permeability
1963 measurement

1964 **Research Procedure Description:** Participants will consume 2 g sucralose and 2 g
1965 erythritol dissolved in 180 mL water. All urine produced over the subsequent 24hr will be
1966 collected.

1967 **Research Related Risks:** Sucralose and erythritol are commonly consumed sugar
1968 substitutes which may cause gas, cramping, diarrhea or bloating in some individuals.

1969 **Measures to Minimize Risks of Harm:** Any participant reporting gastrointestinal
1970 distress following the test will be given the option of not participating in the test at the
1971 next opportunity.

1972
1973 **Research Procedure Name:** SmartPill

1974 **Research Procedure Description:** The SmartPill is an ingestible FDA-approved
1975 wireless motility capsule that transits the gastrointestinal tract while continuously
1976 measuring pH, temperature, pressure, and gastrointestinal transit time. A single pill will
1977 be ingested by volunteers and allowed to pass normally through the gastrointestinal
1978 tract.

1979 **Research Related Risks:** Choking, aspiration, retention gastrointestinal tract.

1980 **Measures to Minimize Risks of Harm:** Potential participants with contraindications for
1981 use will not be allowed to participate in the SmartPill procedure. If they are randomly

1982 selected for SmartPill testing, an alternate will be chosen to participate instead. Pills will
1983 be ingested under staff supervision.

1984

1985 **C6.2 Incidental or Unexpected Findings**

1986

1987 Health problems identified during the screening process will be documented and a copy

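### The follow-up BAL versus NEG BAL comparisons use paired t-tests, which drop any man lacking one phase although the mixed model that gates them can use him; contrasts from that model would be a cheap improvement

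*Combined protocol and SAP*

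**What the plan says.** B5.8.2, Primary Objectives, sets the main analysis: "Linear mixed models will be used to determine main effects of phase (SUSOPS BAL and" SUSOPS NEG BAL), time within phase and their interaction. The follow-up is conditional on that model: when "significant phase-by-time interactions are observed post hoc comparisons will be made" "using paired t-tests with Bonferroni corrections". Under Secondary Objectives the same follow-up is written for the appetite outcomes. For intestinal permeability and transit time it comes after a significant main effect.

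Four other places bear on who has both phases:

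- C3 lets an investigator end a man's part in the "study if the volunteer is unwilling or unable to complete study procedures or follow study" diets or exercise prescriptions. Illness and injury are further grounds.
- C3 also says that on withdrawal all further "data collection will discontinue, but the data that was collected up to the point of withdrawal may" still be analysed.
- B5.8.1 starts from 11 men. "To account for potential attrition (~30% attrition in 16-02-HC"), it adds 4 to reach 15.
- B5.2.2 instead requires 15 men to complete testing, and enrols up to 60 to cover attrition and screening "failures in order to get complete data on 15 subjects".

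The plan gives no missing-data rule, no definition of the analysis population and no sensitivity analysis for withdrawal.

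**The concern.** A man with usable data from only one SUSOPS contributes to the linear mixed model but not to a paired t-test of BAL against NEG BAL. The test that opens the gate and the comparison that locates the difference can therefore be run on different men, and the second group is selected for having got through both phases.

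Primary hypothesis 2 is directional: energy balance should attenuate IL-6 and hepcidin and improve iron absorption compared with deficit. A significant interaction shows only that the two time profiles differ. The size and timing of the diet difference would be read from the follow-up comparisons. If the men who leave tend to be those with larger NEG BAL responses, a completers-only estimate is pulled toward no difference. If they are not, the plan still gives up a little precision that its own model could supply.

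**Working it through.** **Inputs from B5.8.1.** Limiting hepcidin row: mean difference 4.7, SD of difference 4.9, alpha 0.05, power 0.80, n = 11. Attrition is about 30%. Sidedness is not stated, so two-sided is assumed.

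**Reproducing the plan's figure.** d = 4.7/4.9 = 0.959. A two-sided paired t-test (noncentral t) needs n = 11, with power 0.817. This matches the plan. For attrition, 11/0.7 = 15.7, close to the stated 15.

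**How many men can be affected.**

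| Reading | Start | Lost at 30% | Pairs left | Hepcidin power before Bonferroni |
|---|---|---|---|---|
| B5.8.1: attrition inside the 15 | 15 | 15 × 0.3 = 4.5 | 10-11 | 0.77-0.82 |
| B5.2.2: 15 must complete | 15/0.7 = 21.4 | 21.4 − 15 = 6.4 | 15 | 0.93 |

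Both losses are upper figures. Men who leave before SUSOPS 1 data help neither method. Men who leave in Recovery 2 already have both SUSOPS phases. Under B5.2.2 the paired test keeps its 15 pairs, so the issue there is selection rather than power.

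**Case 1: dropout follows a value already observed.** Assumptions: true difference 4.7, SD of differences 4.9, between-phase correlation 0.5, two in-SUSOPS times per phase (within-phase correlation 0.75), enrolment until 15 complete, 3,000 simulated trials, and generalised least squares with known covariance. The log-odds of dropout rise by the slope shown per SD of the early NEG BAL value.

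| Slope | Paired mean (SD) | Model mean (SD) | Paired shortfall from 4.7 | Model SD smaller by |
|---|---|---|---|---|
| 0 | 4.72 (1.26) | 4.71 (1.19) | none | 1 − 1.19/1.26 = 5.6% |
| 1 | 4.39 (1.23) | 4.69 (1.17) | 0.31/4.7 = 6.6% | 1 − 1.17/1.23 = 4.9% |
| 2 | 4.23 (1.22) | 4.66 (1.16) | 0.47/4.7 = 10.0% | 1 − 1.16/1.22 = 4.9% |

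A further simulation with other assumed correlations and slopes gave paired estimates of 4.1-4.3 against 4.7 from the model. At one decimal, 4.1 means a shortfall of 12.8%, or up to 13.8% if the unrounded value is 4.05. Together these give roughly 6-14%. If dropout instead depends on the SUSOPS 1 value, whichever diet came first, the paired estimate is 4.44-4.64, which is 1-6% low.

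**Case 2: dropout unrelated to outcome.** Neither method is biased. Across runs the model's standard error is about 1-7% smaller. The gain shrinks as fewer of the dropouts supply a usable phase.

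**Case 3: dropout follows the NEG BAL response, one value per phase.** Dropout is assumed to correlate 0.5 with that response, at 30% loss and between-phase correlation 0.3-0.6.

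| When men leave | Paired | Mixed model |
|---|---|---|
| Before the NEG BAL value is taken | 3.94-4.15 | 3.81-3.95 |
| NEG-BAL-first men after their NEG BAL value, BAL-first men before it | 4.02-4.20 | 4.33-4.34 |

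In the first row the model is no better than the paired test. A second set of assumptions for that case gave 3.6-4.1 paired and 3.3-3.9 by model. In the second row the model recovers only part of the shortfall.

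**The case against.** The strongest reply is that the mixed model, not the t-test, decides whether there is a diet effect. The paired tests run only after a significant model result and serve to locate the difference. That is right, and a reader who took them as the deciding test would be going beyond B5.8.2. What stands is that the located difference and its estimate come from completers.

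Other stronger readings are also unsupported:

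- **Every paired comparison loses these men.** B5.8.2 does not limit the follow-up to BAL against NEG BAL. Comparisons of times within one phase keep a man who has that phase.
- **The permeability opt-out tracks NEG BAL.** C6.1 says a participant with "distress following the test will be given the option of not participating in the test at the" next opportunity. That is distress after the sucralose and erythritol drink, given on days -1, 4 and 14, so it can arise at baseline or under either diet.
- **The diet effect is understated.** Nothing in the documents says that men who tolerate NEG BAL poorly have larger IL-6 or hepcidin responses. Withdrawal may also be for unwillingness, illness or injury.
- **About six men are lost.** That fits only the 15-completer target in B5.2.2. The section that gives the 30% implies 4-5 of 15.

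It is also fair to say that Case 1 builds in the condition under which the model does well, and that a shortfall of 0.31-0.47 is only about 0.25-0.4 of a standard error of roughly 1.2. A paired t-test also uses its own SD of differences, whereas a model contrast depends on the covariance structure chosen.

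**Conclusion.** The point holds as a cheap improvement, not as a flaw that undermines the primary analysis. The follow-up test is narrower than the model that gates it, for no stated reason. At about 30% attrition it sets aside at most 4-5 of 15 men, or 6-7 of 21-22.

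The consequence depends on why and when men leave, which the documents do not say. If dropout follows observed values, the paired hepcidin estimate is roughly 6-14% low and the model contrast is close to unbiased. If dropout is unrelated to outcome, the only gain is a standard error about 1-7% smaller. If men leave before any NEG BAL sample, both methods are low and the model is slightly worse. The dropout strengths, correlations and sampling patterns are assumptions; only the 4.7, the 4.9 and the 30% come from the plan.

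**What to change.** In B5.8.2, under Primary Objectives and wherever Secondary Objectives repeat the rule, replace the paired t-tests with Bonferroni-adjusted contrasts from the same fitted linear mixed model. Specify:

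1. The model uses every randomised man with any SUSOPS data. This belongs in B5.8.2; the wording in C3 is a permission to keep data, not an analysis rule.
2. The covariance structure allows variance to differ by time, and small-sample degrees of freedom are used.
3. The completers-only paired t-test is reported as a sensitivity analysis.
4. Missing phases are tabulated by diet and reason.
5. A separate sensitivity analysis addresses withdrawal during NEG BAL, for example by shifting the unobserved NEG BAL values over a stated range and reporting how the contrast moves. The model contrast alone does not cover this case.

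Also reconcile B5.8.1 (15 including attrition) with B5.2.2 (15 completers), so that the expected number of pairs is clear.

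The cost is analysis-plan wording and a few extra tables; the contrasts come from models already planned, and no new visits or samples are needed. The downside is reliance on missing-at-random and on the model's covariance structure.
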